4.4.3 Optimal Overall Response: All Timepoints

Once all data of a patient are available, its optimal overall response may be determined.

Evaluation of the optimal overall response when it is not required to confirm complete or partial response effects in the study: During the trial, the optimal response effect is the optimal effect at all timepoints (for example, one patient is evaluated as with SD during response evaluation in the cycle 1, PR in cycle 2, and PD in the final cycle, so his/her optimal overall response is evaluated as PR). When the optimal overall response is evaluated as SD, it must meet the minimum time counted from baseline, as specified in the protocol. If it does not meet the criteria for the minimum time, it is not acceptable even the optimal overall response is evaluated as SD, and the optimal overall response of the patient will be determined, based on subsequent evaluations. For example, one patient is evaluated as with SD in cycle 1 and PD in cycle 2; however, it does not meet the requirements for the minimum time of SD, so his/her optimal overall response is evaluated as PD. Meanwhile, if a patient is evaluated as with SD, and then is lost to follow-up, the patient will be regarded as not evaluable.

Evaluation of the optimal response when it is required to confirm complete or partial response effects in the study: It may be stated as complete response or partial response only when each subject complies with the criteria for partial or complete response, as specified in the trial, and a further response confirmation is conducted at subsequent timepoints (generally 4 weeks later) as mentioned in the protocol. In such case, see the explanations in Table 3 for the optimal overall response.

4.4.4 Special Hints for Response Evaluation

When nodular lesions are included in the evaluation of total target lesions, and meanwhile the node size is reduced to "normal" size (<10 mm), they will have a scanning report for lesion size. To avoid overestimation of the condition reflected on the basis of increased node size, the measurement results will be recorded, even though the node is normal. As mentioned previously, this means subjects with complete response will not be recorded as 0 in CRF/ECRF.

If it is required to confirm response during trial, optimal response evaluation will be complicated by repeated "immeasurable" timepoints. The analysis plan of the trial must

clarify that, those missing data/evaluations may be explained clearly in determining response. For example, in the majority of trials, the PR-NE-PR response of a patient may be regarded as response confirmation obtained.

When the whole healthy condition of a subject develops exacerbation and it is required to discontinue medication, but there is no objective evidence, it will be reported as symptomatic progression. Even after termination of treatment, objective progression shall be evaluated as far as possible. Symptomatic progression is not an evaluation description of objective response: It is the reason for discontinuation of the treatment. The objective response in those subjects will be evaluated by target and non-target lesions as shown in Tables 1-3.

Those defined as early progression, early death, or non-evaluability are particular cases of the study, and shall be described clearly in each protocol (depending on treatment interval and treatment cycle).

In some cases, it is difficult to differentiate local lesions from normal tissues. If the evaluation of complete response is based on this definition, we recommend to carry out a biopsy prior to response evaluation of complete response of local lesions. When the abnormalities in the radiological examination results in some subjects are regarded as representing lesion fibrosis or scar formation, FDG-PET is taken as a similar evaluation standard to biopsy, and is used to confirm response of complete response. In such case, FDG-PET use shall be described prospectively in the protocol, and meanwhile the reports from specialized medical literatures aiming at such case are used as supportive evidence. However, it must be realized that, it will result in false positive results of complete response evaluation, due to restrictions of FDG-PET and biopsy (including extent of resolution and sensitivity for both of them).

Table 1 Timepoint Response: Subjects with Target Lesions (including non-target lesions or not)

Target Lesion	Non-Target lesions	New Lesions	Overall Response
CR	CR	No	CR
CR	Non CR/Non PD		PR
CR	Not evaluable		PR
PR	Non-progressive or not completely evaluable	No	PR
SD	Non-progressive or not completely evaluable	No	SD
Not completely evaluable	Non-progressive	No	NE
PD	Any situation	Yes or No	PD
Any situation	PD	Yes or No	PD
Any situation	Any situation	Yes	PD

CR = complete response	PR = partial response	SDStable disease	PD = progression of disease NE = not evaluable
------------------------	-----------------------	------------------	---

In SD patients, at least one follow-up measurement after enrolment must meet the SD criteria, and follow-up and enrolment are separated by at least 6-8 weeks.

Table 2 Timepoint Response - Subjects with only Non-target Lesions

Non-Target lesions	New Lesions	Overall Response
CR	No	CR
Non CR or non PD	No	Non CR/Non PD
Not completely evaluable	No	Not evaluable
Unclear PD	Yes or No	PD
Any situation	Yes	PD

Notes: For non-target lesions, "non CR/non PD" are responses better than SD. As SD has been used more and more as endpoint variable, it is aimed at the situation there is no measurable lesions, to set up the non CR/non PD response. For unclear progression findings (such as very small, undetermined new lesions, or cystic degeneration or necrosis or original lesions), the treatment may be continued to the next evaluation. If progression of disease is confirmed in the next evaluation, then the progression date is that date when the suspected progression occurs.

Table 3 Optimal Overall Response for confirmation of CR and PR

Overall Response at the first timepoint	Overall Response at subsequent timepoints	Optimal Overall Response
CR	CR	CR
CR	PR	SD, PD or PR ^a
CR	SD	If SD persists for sufficient time, then it is SD, otherwise it is PD.
CR	PD	If SD persists for sufficient time, then it is SD, otherwise it is PD.
CR	NE	If SD persists for sufficient time, then it is SD, otherwise it is NE.
PR	CR	PR
PR	PR	PR
PR	SD	SD
PR	PD	If SD persists for sufficient time, then it is SD, otherwise it is PD.
PR	NE	If SD persists for sufficient time, then it is SD, otherwise it is NE.
NE	NE	NE

Notes: CR is complete response, PR is partial response, SD is stable disease, PD is progression of disease, and NE is not evaluable. Superscript "a": If CR occurs actually at the first timepoint, then for any disease occurs at subsequent timepoints, its response evaluation is still PD at subsequent timepoints (as the disease will occur again after CR), even though the response evaluation of the subject does not meet the PR criteria. Optimal response is dependent on whether SD occurs at the minimum treatment interval. Nevertheless, sometimes it is evaluated as CR, but a scan suggests that small lesions seem to occur still at subsequent timepoints; therefore actually, the patient's response is PR other than CR at the first timepoint. In such case, the first CR judgment shall be revised as PR, and meanwhile the optimal response is PR.

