3.1 SUMMARY OF EXPERIMENTAL DESIGN

3.1.1 Rationale for Study Design

This is a bicentric, open-label, phase Ib clinical trial comparing the safety and efficacy of two different administration methods of Fruquintinib in patients with advanced colorectal cancer after failure of standard care, as to further determine the recommended dose and administration method for phase II/III clinical studies.

This trial is comprised of two parts: randomized comparison part and expansion part.

Randomized comparison part: patients will be randomized into Group A or B after meeting the screening criteria.

Group A: Fruquintinib 4mg qd po, daily, until progression of disease, unacceptable toxicity or voluntary withdrawal from the trial in advance.

Group B: Fruquintinib 5mg/ qd po, 3-week on/1-week off, until progression of disease, unacceptable toxicity or voluntary withdrawal from the trial in advance.

28 days is one cycle of Fruquintinib treatment. Information on the subsequent antitumor therapy will be collected for the patient after progression of disease, unacceptable toxicity or voluntary withdrawal from the trial, and the patient's survival status will be followed up until death.

Expansion part: the recommended dose for phase II/III studies is determined for the expansion part based on the randomized comparison part.

3.1.2 Rationale for Dose Selection.

(1) Safety dose:

Phase I clinical tolerability study of Fruquintinib: A single dose within the range of no more than 6.0mg could be tolerated, and higher doses were not explored. Multi-doses of Fruquintinib once daily were given for consecutive 28 days in the phase I tolerability clinical trial, the main dose limiting toxicity (DLT) was hand-foot syndrome. Grade 3 hand-foot syndrome limited the subjects to receive 6.0mg dose and **the maximum tolerated dose was 4.0mg.**

Expansion part of administration for 3-week on/1-week off: 5.0mg and 6.0mg could be

tolerated, and higher doses were not explored. Only one DLT of asthenia occurred in 6.0mg dose group.

(2) Efficacy during the whole phase I tolerability trial:

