Information on subsequent treatment												X
Survival:											X	X

Notes:

- The baseline tumor assessment will be done within 2-3 weeks prior to administration, four sites (neck, chest, abdomen and pelvis) are evaluated in accordance with

RECIST1.1 criteria. Using the radiological (CT/MRI) examination, the baseline evaluation and post-treatment efficacy evaluation are performed with the same method and by the same investigator; tumor radiological assessment (CT or MRI) is performed every two cycles of treatment (8 weeks), until progression of disease. If the tumor is assessed as complete response or partial response (CR or PR), it needs to be re-confirmed 4 weeks later. If the subject receives the drug for less than 56 days, tumor assessment could be performed at the end of medication when necessary, according to investigator's judgement.

2. The vital signs include blood pressure, heart rate, respiratory frequency and temperature, and are monitored 2 hours(\pm 1 hour) after administration;
3. Hematological examination: red blood cell, hemoglobin, platelet count, neutrophil and its differential categories; prothrombin time (PT), activated partial thromboplastin time(APTT), thrombin time(TT), fibrinogen quantification(FIB) and INR. If the neutrophil is $\leq 1 \times 10^9/L$ or platelet count is $\leq 25 \times 10^9/L$, the frequency of repeated testing needs to be increased (once/2-3 days);
4. Serum chemistry: if 3 times elevation of ALT or AST occur during the trial, the frequency of repeated testing needs to be increased (2-3 times/week advised); the creatinine clearance at baseline is calculated based on the creatinine level (formula: $Ccr = (140 - \text{age}) \times \text{body weight}(\text{kg}) / [72 \times \text{Scr}(\text{mg/dl})]$ or $Ccr = [(140 - \text{age}) \times \text{body weight}(\text{kg})] / [0.818 \times \text{Scr}(\text{umol/L})]$, the unit of creatinine should be noted during the calculation of creatinine clearance, the result for female is the calculated result $\times 0.85$);
5. Routine urinalysis is used for measurement of urine protein, and needs to be repeated when urine protein ++ occurs once, 24-hour urine protein quantification is required for urine protein++ in consecutive two measurements;
6. 12-lead ECG is performed in screening period, 4 hours(\pm 1 hour) after administration on Day 7, 14, 21 and 28; and by the frequency of follow-up from the 2nd cycle of therapy;

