6.2.1.2 Assessment of effectiveness

The tumor is evaluated in accordance with RECIST1.1 criteria, and the detailed evaluation criteria are provided in Appendix 2. The radiological evaluation of tumors could use CT or MRI as decided by investigators, however, the apparatus and technical parameters should keep consistent throughout the study; contrast agent should be used in case of no contraindications. If the tumor evaluation has been performed 14-21 days before the first dose, and the same method and apparatus are used in the same hospital, this evaluation could be used as the baseline tumor evaluation. The baseline tumor evaluation should include neck, chest, abdomen, pelvis and any other sites that are suspected to have tumor lesions. Bone scan should be used for follow-up of the disease in patients with bone metastasis.

Record of target lesions: number, site and description of lesions, the maximum diameter measured for each lesion (except lymph node) and the minimum diameter measured for lymph node, sum of diameters including all the target lesions;

Subjects will receive the first tumor evaluation after 2 cycles of treatment, and one evaluation every two cycles subsequently, until progression of disease. If complete response or partial response occurs, it needs to be confirmed after 4 weeks. If the patient interrupts the dose for adverse drug reaction or other reasons, the tumor evaluation will be performed once every 8 weeks as originally scheduled. If the patient discontinues the study drug within 56 days, the tumor evaluation should be performed as early as possible after discontinuation of the drug.

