8.1 Primary and secondary research variables

Primary variables:

Overall incidence of adverse events

Incidence of Grade 3/4 adverse events

Incidence of serious adverse events

Incidence of adverse events leading to permanent discontinuation

Incidence of adverse events leading to interruption/reduced dose

16-week progression-free survival rate

Secondary variable:

Effectiveness:

"Event occurrence date" variable: Calculated since the day when the informed consent is signed. If no event is observed, there is no date of end, and a so called cutoff observation has to be considered for analysis. The cutoff date is: The last date, such as for "last tumor measurement", "last medication registration", or "last visit".

Secondary efficacy variables include objective response rate, disease control rate, duration of response, progression-free survival, and overall survival.

Objective response rate (ORR): defined as the incidence of confirmed complete response (CR) or partial response (PR), the target lesions and non-target lesions are evaluated with validated radiological method and judged in accordance with RECIST criteria 1.1.

Progression-free survival (PFS): defined as the time from the signature of informed consent form to the first recording of progression of disease (PD) or date of death, whichever comes first. If no PD is observed, the censoring date should be the date of the last tumor measurement.

Overall survival (OS): defined as the time from the signature of informed consent form to date of death for any reason. If no death is observed, the last follow-up date is regarded as the censoring date.

Disease control rate (DCR): defined as the incidence of confirmed complete response (CR), partial response (PR) and stable disease (SD), the target lesions and non-target lesions are

evaluated with validated radiological method and judged in accordance with RECIST criteria 1.1.

Duration of response: defined as the time from the first recording of CR or PR to the first finding of PD for patients who have achieved response. For those with no record of PD after CR or PR, the censoring date is the date of the last tumor measurement.

Safety and Tolerability:

Safety and tolerability of the treatment are evaluated by incidence and severity of adverse events, laboratory tests, vital signs, ECG, LVEF, and ECOG performance status.

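### Flowchart Note 1 makes the scan after an early stop optional, against section 6.2.1.2, so failing patients could be censored at baseline in the expansion part's primary 16-week PFS rate

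*Protocol*

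**What the plan says.** Three places govern whether a patient who stops early is scanned.

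- Study Flowchart, Note 1 (section 6), for a patient on drug for less than 56 days: "tumor assessment could be performed at the end of medication when necessary, according to investigator's judgement".
- Section 6.2.1.2, for a patient who discontinues within 56 days: "the tumor evaluation should be performed as early as possible after discontinuation of the drug".
- Appendix 2, section 4.4.4, for a patient whose general condition worsens without objective evidence: "Even after termination of treatment, objective progression shall be evaluated as far as possible". The same paragraph adds: "Symptomatic progression is not an evaluation description of objective response: It is the reason for discontinuation of the treatment".

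Two rules in section 8.1 then decide how that patient enters PFS. The event runs "to the first recording of progression of disease (PD) or date of death, whichever comes first". For the rest: "If no PD is observed, the censoring date should be the date of the last tumor measurement".

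The 16-week PFS rate is a primary variable in section 8.1, and section 6.2.1.1 makes PFS at Week 16 the primary effectiveness endpoint of the expansion part, a single arm of about 20 patients. Section 8.2.2 says only that the rate is calculated. It does not name Kaplan-Meier or a proportion, and it does not say whether patients without a post-baseline scan stay in the denominator.

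**The concern.** A site that follows Note 1 and a site that follows section 6.2.1.2 are both complying with the protocol, yet they can produce different endpoint data for the same patient.

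Take a patient who deteriorates and stops in week 5. If scanned, PD can be recorded and the patient is a failure. If not scanned, there is no PD, the last tumor measurement is the baseline scan, and that scan was taken before the first dose. Unless a death or a later PD is recorded, the patient contributes no follow-up to a Kaplan-Meier estimate. The trial is open-label, so the person who decides whether to scan knows how the patient is doing.

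Kaplan-Meier treats a censored patient as having the same later risk as those still followed. A patient who stopped because of clinical worsening does not have that risk. The endpoint exposed is the primary efficacy result of a small single-arm part, where one patient in 20 is five percentage points. No later analysis can recover a scan that was never taken.

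**Working it through.** **No planned figure to reproduce.** The protocol states no target 16-week rate, precision or power for the expansion part, so the calculation is illustrative.

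**Inputs**

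- n = 20, the approximate size of the expansion part (section 8.3).
- True 16-week PFS rate = 50%, an assumption. It agrees with the interim median PFS of 3.7 months in the 3-week-on/1-week-off group (section 3.1.2) if PFS is exponential: 16 weeks = 112/30.4375 = 3.68 months, and 0.5^(3.68/3.7) = 50.2%.
- k = number of true failures who stop before Day 56, are not scanned and have no recorded PD or death. The documents give no figure. The range 0 to 5 is an assumption.

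**Kaplan-Meier with k patients censored at baseline**

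Ten patients are truly progression-free at Week 16 and ten fail. The k censored patients leave before the first event time, so 20 − k remain at risk and 10 − k failures are observed. With no other censoring before Week 16 the estimate telescopes to

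S(16) = 10/(20 − k).

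Example for k = 3, with five true failures by Week 8 and five by Week 16: (15/17) × (10/15) = 10/17 = 58.8%. How the failures divide between the two scans does not matter.

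| k | Kaplan-Meier, censored at baseline | All 20, unscanned counted as failures |
|---|---|---|
| 0 | 10/20 = 50.0% | 50.0% |
| 1 | 10/19 = 52.6% | 50.0% |
| 2 | 10/18 = 55.6% | 50.0% |
| 3 | 10/17 = 58.8% | 50.0% |
| 4 | 10/16 = 62.5% | 50.0% |
| 5 | 10/15 = 66.7% | 50.0% |

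The estimate is the true rate multiplied by 20/(20 − k), so the relative inflation does not depend on the 50% assumption: 1.05, 1.11 and 1.18 for k = 1, 2 and 3.

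**What removes the bias**

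- The scan is done and shows PD: all ten failures are observed and the estimate is 50.0%.
- The unscanned patient dies by Week 16 and the death is counted: again 50.0%.
- The rate is a proportion of all 20 with unscanned patients as failures: 50.0% (last column).

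A death after Week 16 does not help. The event is then dated after Week 16, so the patient counts as progression-free at that time: (10 + k)/20 = 55%, 60% or 65% for k = 1, 2 or 3.

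**The case against.** The case on the other side is substantial and limits the point.

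- **The scan is asked for.** A reader might infer that the protocol exempts early stoppers from a scan. It does not. Section 6.2.1.2 and Appendix 2 both call for one, and only Note 1 is permissive. What stands is that the documents disagree.
- **The response criteria are not at fault.** A reader might take the Appendix 2 sentence on symptomatic progression as an error. It is part of the adopted RECIST 1.1 text. Counting symptomatic progression as failure is a legitimate supporting analysis, not a correction of the criteria.
- **Failing patients do not simply vanish.** Death is a PFS event, and section 3.1.1 says "the patient's survival status will be followed up until death". A death by Week 16, or a later scan with PD, brings the patient back as an event. This stands, so the bias needs all of these to be absent.
- **The estimator is not stated.** Section 8.2.2 lists Kaplan-Meier for PFS under the randomized part. For the expansion part a proportion over all patients is equally open, and it need not be inflated. So inflation cannot be stated as a fact.
- **After Day 56 the conflict ends.** A reader might extend the argument to patients who worsen after the first scan. Note 1's optional clause covers only those on drug for less than 56 days. For later patients both places require scans every two cycles, in section 6.2.1.2 as "one evaluation every two cycles subsequently, until progression of disease", with no exception for having stopped the drug.
- **The frequency is unknown.** Section 3.1.2 reports 17 and 18 evaluable patients of 20 per group at the interim. The reasons are not given, those patients were in the randomized part, and the same section reports 7 and 4 permanent discontinuations for toxicity, which could explain them. This does not show that any patient stopped for symptomatic progression without a scan.
- **The SAP may settle the analysis.** Section 8.2.3 defers detail to a SAP that is not at hand. That holds for supporting analyses. It does not hold for Note 1, which governs data collection, or for the censoring rule, which section 8.1 fixes.

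**Conclusion.** The contradiction between Note 1 and section 6.2.1.2 is real and bears on the ascertainment of the expansion part's primary efficacy endpoint. Together with the censoring rule in section 8.1 it opens a route to informative censoring at baseline.

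Whether the 16-week rate is biased is conditional on four things: the patient stops before Day 56 and is not scanned; the patient is in fact progressing; no PD is recorded later and no death occurs by Week 16; and the rate is estimated by Kaplan-Meier. Under those conditions the bias is upward, by about 3 points for one such patient in 20 and about 9 points for three at an assumed true rate of 50%. If the scan is done and shows PD, or unscanned patients count as failures over all 20, it is zero. The documents do not support a claim that clinical failures are removed from the endpoint as a rule, or that the rate will be inflated.

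**What to change.** 1. Reword Study Flowchart Note 1 to match section 6.2.1.2: every patient who stops before Day 56 has the tumor evaluation after discontinuation, unless dead or refusing.
2. In sections 8.1 and 8.2.2, state that the 16-week PFS rate is taken over all treated expansion patients. Add a supporting estimate in which early stoppers without a post-baseline scan count as not progression-free. If the SAP already contains this, a cross-reference is enough.

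The cost is a few sentences. The scan adds nothing to what section 6.2.1.2 already asks for. The downside is that the reported rate may be a few points less favourable.
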